3.6 GEBT Administration – Final Video Call

3.6.1 Approximately 5 minutes after the 240-minute breath sample should have been collected, send the following text and start the video call in TigerConnect using Text Message Template 12 (already set up in TigerConnect).

Text Message Template 12

"To complete your GEBT, please select the secure link to video chat in the next text to speak with your tele-administrator."

3.6.2 Complete the test administration by reviewing all paperwork, covering the points below, and explaining how to package the breath samples.

- *Confirm the patient has collected all scheduled breath samples*
- *Review patient test request form*
- *Check that all information has been entered - including units of measure for height and weight*
- *Confirm Patient's Signature*
- *Confirm start and finish test-meal consumption times are recorded*
- *Confirm actual post-meal breath collection times are recorded and are within the +/- 5-minute time frame.*
- *View breath samples for condensation and sharpie check marks*
- *Proper packaging for return to lab*
- *Ensure test request form is placed into bubble mailer.*
- *Ask again if there are any questions and document questions/answers*
- *TA will need to encourage the patient to ship the samples back to us within 3 days, stressing that the quicker we receive them, the quicker we can analyze them and send the results to their physician.*

3.6.3 Inform the patient that after we receive the samples, the results should be uploaded to their physician within 2 business days.

3.6.4 Initial and date on FORM-CD-037, "Meal Administration Questionnaire & Checklist."

3.6.5 After completion of the tele-administration, the CSR/CSM will initial/date FORM-CD-036, "Telehealth Patient Contact Form."

CAIRN DIAGNOSTICS	DOC No. SOP-CD-028.00
SOP: Telehealth Administration Procedures	Page 6 of 7

3.6.6 After the patient has packaged the breath samples, schedule the following text for the next day (NOTE: Insert the shipping company name that is used for shipping):

Text Message Template 13

"Please confirm you dropped off the sample with (insert shipping company name) to be shipped to Cairn Diagnostic Laboratory. Reply with a YES or NO."

3.6.7 If the patient replies, yes, then initial and date "Breath Sample Shipping Confirmation Received" on FORM-CD-036, "Telehealth Patient Contact Form." If the patient replies no, call the patient to determine why the breath samples have not yet been shipped and attempt to help expedite return of the breath samples.

3.6.8 Once breath samples are received initial/date FORM-CD-036, "Telehealth Patient Contact Form."

4.0 REFERENCES

- A. SPEC-CD-037 Telehealth Physician Order Form
- B. FORM-CD-036 Telehealth Patient Contact Form
- C. FORM-CD-037 Telehealth Meal Administration Questionnaire & Checklist
- D. SOP-CD-009 Commercial Accounts Setup
- E. SOP-CD-023 GEBT Order Placement
- F. SOP-CD-033 Operation and Administration of the TigerConnect Telehealth Platform
- G. SPEC-CD-016 Telehealth Patient Brochure
- H. SPEC-CD-032 Telehealth GEBT Patient Preparation Sheet
- I. SPEC-CD-033 Telehealth GEBT Intended Use, Contraindications, Warnings and Precautions
- J. SPEC-CD-038 GEBT Informational Video

5.0 EXHIBITS

- A. Patient Welcome Call Script
- B. Telehealth Administration Call Script
- C. Summary Email Template

CAIRN DIAGNOSTICS	DOC No. SOP-CD-028.00
SOP: Telehealth Administration Procedures	Page 7 of 7

6.0 REVISION HISTORY

Revision Level	Brief Description of Revision(s)	Effective Date
00	Initial revision.	See the first page of this document.

UNCONTROLLED COPY
Version May Not Be Current

CAIRN DIAGNOSTICS	DOC No. SOP-CD-028.00 EXHIBIT A
SOP: Telehealth Administration Procedures EXHIBIT A: PATIENT WELCOME CALL SCRIPT	Page 1 of 2

Welcome Call Script:

Phone call to patient after receiving Telehealth Physician Order Form

Good morning/afternoon. My name is "CSM/CSR Name" with Cairn Diagnostics, May I speak with Jane Doe?

[name], I am calling to schedule your Gastric Emptying Breath Test, AKA GEBT, ordered by Dr. _____. It will take about 5 minutes to schedule your procedure.

Great! To get started, I need to verify some information (*which is found on the Physician Order Form*). Please confirm your:

- Name
- DOB
- Shipping address for kit shipment
- Mobile phone number
- Email

The GEBT test will be conducted at your home using a secure video link. I need to ask you a few questions to be sure we are able to conduct the GEBT at your home under the direction of one of Cairn Diagnostic's tele-administrators. (*Record on the Telehealth Patient Contact Form, FORM-CD-036*)

1. Is your mobile phone able to send and receive text messages?
2. Do you have a Smartphone/tablet/iPad or laptop with audio/video capabilities and internet access at home? What device do you plan on using for the tele-administration of the GEBT? (*choices are smartphone, tablet, or laptop*)? (*Ask what device will be used and enter on the form*)
3. Do you have a microwave that you can use on the day of the test?
4. If you are an insulin dependent diabetic, will someone be able to accompany you, or check on you, during the test?
5. After the test is finished you will need to send your breath samples back to us in a prepaid bubble mailer, which will be included in the GEBT kit. We usually use UPS. Do you have access to a UPS store nearby or do you live in a building which offers UPS pickup? (*CSR may have look up the nearest UPS drop-off location <https://www.ups.com/dropoff/>. If UPS dropoff/pickup is not available, contact the shipping department for an alternative method.*)

(If the answer to questions 1-5 are all Yes, continue; if no to any one question, stop and reschedule.)

Ok, now let's get you scheduled. You will need to set aside approximately 5 hours to complete the test. Our next available appointment is "Day, Date and Time of appointment" (e.g., Friday, August 3, 2020 at 7 am).

You will receive a text message confirming your appointment. You will also receive an email that will include the Telehealth GEBT Patient Preparation Sheet that **must be reviewed prior to the morning of the test. It will also be provided with your kit. There are certain items that you are required to have to complete the test that are not included in the test kit.** Within this

same email you will receive a link to our patient informational video which discusses what to expect when taking the GEBT at home.

Your GEBT Kit will be shipped to the address we confirmed earlier. You will receive an automated text when the kit has been shipped, which will include the tracking number and an approximate delivery date. We will send a follow-up text within 2 or 3 days to verify that you have received the kit.

The day before your test you will receive a text message reminder. **Please be sure to review the patient preparation sheet and the patient informational video!** Thank you for scheduling your test. Do you have any additional questions? (note any questions asked and answers given)

UNCONTROLLED COPY
Version May Not Be Current

CAIRN DIAGNOSTICS	DOC No. SOP-CD-028.00 EXHIBIT B
SOP: Telehealth Administration Procedures EXHIBIT B: TELEHEALTH ADMINISTRATION CALL SCRIPT	Page 1 of 8

Step	Tele-Administrator	Form Location	Notes
1	Good Morning, my name is (Tele-administrator Name), and I will be your tele-administrator for the GEBT. Before we start, I have a few things I need to confirm.		
2	Please verify your Name and Date of Birth. I also need to verify your identity. Would you show me a picture ID such as your driver's license, etc.?	Section 1 Question 1	Verify that the Name and DOB on the order form matches their answer. If it does not match write in the correct information on the form
3	Did you receive the GEBT Test Kit? Would you read to me or show me the barcode number on the right-hand side of the kit box?	Section 1 Question 2	This should have been confirmed ahead of time through shipping and patient text confirmation.
4	What is the kit lot number and expiration date that are printed on the label on the left hand side of the kit box?	Section 1 Question 3	If the kit has an expired lot number, do not proceed with the test
5	Do you feel well enough to take the GEBT Test this morning?	Section 1 Question 4	If not, reschedule the test
6	Have you completed an 8-hour overnight fast?	Section 1 Question 5	If not, reschedule the test
7	Are you diabetic? (If yes) What is your blood glucose this morning?	Section 1 Question 6	*If patient's blood glucose level is >275 mg/dL, reschedule the test.
8	Do you have anyone assisting you with this test today?	Section 1 Question 7	*If they are diabetic and this response is NO, reschedule the test.
9	Did your doctor advise you to stop taking any medications that could affect your gastric emptying rate prior to your test? (If yes) Have you done so?	Section 1 Question 8	*If NO patient must reschedule test

CAIRN DIAGNOSTICS	DOC No. SOP-CD-028.00 EXHIBIT B
SOP: Telehealth Administration Procedures EXHIBIT B: TELEHEALTH ADMINISTRATION CALL SCRIPT	Page 2 of 8

Step	Tele-Administrator	Form Location	Notes
10	Have you received any other breath tests within the past 24 hours? If so, what was the test?	Section 1 Question 9	If the patient received another ¹³C breath test in the last 24 hours, reschedule the test.
11	Are you able to sit in a quiet area and refrain from vigorous activity or exercise for the duration of the test?	Section 1 Question 10	If not, reschedule the test.
12	Remember that you may not eat, drink, or smoke while taking the GEBT.		
13	If we lose connection, I will call you to determine the reason for the lost connection. I will then send you a new video link. Please ensure that your phone, tablet, or laptop is charged or plugged into power and connected to a reliable Wi-Fi/internet connection. At the end of your last breath sample we will send you another video link to make sure you package the samples correctly for UPS. At this point you will be finished. Please plan for 5 hours.		If the patient or administrator loses the connection and cannot regain a video connection, continue with a phone call explaining the procedure over the phone, if the test meal pouch and crackers have not been opened, then you may need to reschedule if unable to establish video connection.
14	Let's begin the GEBT Administration		
15	Please wash your hands before beginning.		
16	Open the GEBT kit by breaking the red seal on the box.		

Step	Tele-Administrator	Form Location	Notes
17	
Remove kit components from box. Can you confirm the following items are in the box?
 
 • 2 straws • Utensils (fork, knife, spoon, & napkin) • Large white cooking cup • 3 oz. pouring cup • 8 test collection tubes in test tube holder • 6 saltine crackers (foil pouch containing 3 packages of 2 crackers each) • ¹³C Spirulina GEBT test meal (Foil pouch containing Spirulina/egg mix) • Test Request Form • Return pre-paid mailing envelope • Package insert information sheet • GEBT Administration Instructions 	Section 2 Question 1	
18	
Fill out the ¹³C-GEBT Test Request Form. Be sure to complete your name, the test administrator's name which is (tele-administrator's name), date of the test which is (today's date), and your age, height, weight, and gender. Please ensure you indicate whether you measured your height and weight in inches and pounds or meters and kilograms. Please hold your insurance card up to the camera so I can verify your insurance information. Please sign and Date the Test Requisition Form.
		
The insurance information should be with the order form but if it is not, then either copy the information on the front/back of the card or see if they can take a picture of the front/back of the card and send via the texts from TigerConnect.

Step	Tele-Administrator	Form Location	Notes
19	Hold the breath collection tube holder in the upright position, open from the front and fold backwards to connect the tab of flap into the slit in the back of tube holder. This will enable the tube holder to stand upright.		Make sure that the tube holder is upright via the video link; otherwise the tubes could fall on the floor.
20	There are (2) pre meal breath test tubes capped in BLUE tops. There are (6) post meal "white capped" test tubes in different time slots, we will be collecting breath samples before and after you consume the meal.		
21	Next, unwrap a straw. You will use the same straw for the entirety of the test. There are two straws in case you need to use an additional straw. Please do not throw the straws away until the last breath sample has been collected.		
22	I will now demonstrate how to collect a breath sample, and you can practice before we start the test.		
23	Unscrew the first blue capped tube and insert the red straw. Inhale and hold your breath for about 5 seconds, then slowly exhale into the test tube while removing the straw at the same time. Replace the cap on the tube (ensure the cap is secure, but do not overtighten). Record the exact time that the samples were collected on the test request form		
24	Please check to see if there is condensation in the test tube. If you feel you did not get a good sample breath, you can redo the breath sample into the same test tube.		

CAIRN DIAGNOSTICS	DOC No. SOP-CD-028.00 EXHIBIT B
SOP: Telehealth Administration Procedures EXHIBIT B: TELEHEALTH ADMINISTRATION CALL SCRIPT	Page 5 of 8

Step	Tele-Administrator	Form Location	Notes
25	Use a marker (sharpie) to put a check mark on the top of each test tube used to collect a breath sample as soon as you have collected that sample or turn the tube upside down in the tube holder. This will help to ensure that you don't collect a breath sample in a tube that has already been used.		
26	If you have not done so, replace the breath sample back into the first slot in the breath tube holder.		
27	Repeat the process with the second "blue capped" pre meal breath sample tube, cap and replace in the second slot. Record the sample collection time. Again, you may check off the tube cap with a marker or place the tube upside down.		Instruct the patient to make sure the breath tubes are in upright position before shipping back to us.
28	
Next, we are going to start the meal preparation.
 
You will need the following:
 
Provided with the GEBT kit
 
 • Cooking cup (large white cup), • 3 ounce pouring cup, • ¹³C-Spirulina GEBT Test Meal pouch • Spoon from utensil packet • 3 packets of saltine crackers 
Not provided with the GEBT kit
 
 • Water • Microwave • Plate • Cup or glass with 6 ounces of water-to drink during test meal 		
29	Open the GEBT meal pouch and remove the oxygen absorber.		

Step	Tele-Administrator	Form Location	Notes
30	Please empty packet into white cooking cup. The powder mix will look yellow/green in color.		
31	Add 3 ounces of water (use 3 oz pouring cup) into cooking cup		
32	Use the spoon to stir the mixture		
33	Place cooking cup into microwave Cook for 1 minute Remove from microwave. Use Caution: Cup may be hot. Flip the partially cooked egg with the spoon and cook for an additional 30 seconds. It is ok if the egg breaks apart while flipping. Use Caution: The egg will be hot.		The egg may be cut into two pieces in order to flip it; make sure they don't flip it onto the floor.
34	Flip the cup upside down on your plate and remove the cooking cup. You may cut the egg meal into pieces to help it cool.		
35	Open the crackers (6) and place on the plate		
36	Use the 3 oz measuring cup to measure 6 ounces of water into your cup or glass		Make sure the patient has meal ready, utensils out, water poured before starting the meal so there is no delay during the meal ingestion.

Step	Tele-Administrator	Form Location	Notes
37	
Next, I want you to consume the test meal
 
The whole meal (egg mix, crackers and water) needs to be consumed within 10 minutes for accurate test results.
		
Encourage the patient to consume all the meal in the 10 minutes! Eat steady and don't distract them during the meal including anyone assisting them.
 
TA will time the meal consumption to verify that it was completed in 10 minutes.

38	
When you are ready to begin eating, record the time from the clock, watch or other device you will use for keeping track of the time during the test on your test request form.
 
Record the time that you finished consuming the test meal on the test request form
	Section 2 Question 2	
39	Now we need to calculate the planned breath collection times.	Section 2 Question 3	
Administrator now calculates post-meal breath sample collection times using the meal finish time and the GEBT calculator; record calculated collection times on Telehealth Meal Administration Questionnaire & Checklist, FORM-CD-037)

Step	Tele-Administrator	Form Location	Notes
40	Please record the post meal collection times that I read off to you in the planned collection times section of your test request form.		Administrator tells patient to record the calculated post-meal collection times on the patient's test request form.
41	I am going to set up automatic patient reminder breath collection texts for breath sample collection times. Although I will schedule the text messages, you will need to make sure to keep track as well so that you take the breath samples at the planned collections times.		Schedule the post-meal text message reminders in TigerConnect; they should be scheduled for 5 minutes before the planned times.
42	Collect post meal breath samples in white capped tubes in the same way as you collected the pre-meal samples in the blue capped tubes. Be sure to collect each breath sample in the correctly labeled tube (e.g., 45 minute sample in tube labeled 45 minutes) and don't forget to mark the cap with a marker when you have collected each sample or turn them upside down in the tube holder, so that you don't accidentally collect a two samples in one tube!		
43	Record the actual time at which you collect each breath sample on the test request form. Breath samples must be collected within 5 minutes of the planned collection time for the results of the test to be accurate!		
44	After you collect your final breath sample at _____ time, I will send you a text message or an email containing a video link so that I can check your test request form and explain shipping instructions for your breath samples.	Section 3 Questions 1-7	Schedule the reminder texts for collecting breath samples in TigerConnect using the text templates (see Section 3.6)

----- END OF VIDEO CALL -----

Dear _____,

It was a pleasure speaking with you this morning. Your test is scheduled for _____ (date) at _____ (time). Please watch the patient information video prior (link included below) to the morning of your scheduled test. The password to view the video is "tummy." <https://cairndiagnostics.com/healthcare-providers/telehealth-resources/> Please review the information below and feel free to contact us if you have any additional questions.

When you receive the kit, do not open the GEBT kit before your virtual meeting with your tele-administrator! Store the GEBT kit in a cool dry place until you are ready to take the test.

Patient Preparation

- The GEBT must be taken after an overnight (minimum eight (8) hours) fast. This means that you must not consume any food or drink, including alcohol and coffee for at least eight (8) hours prior to starting the test.
- You may consume a small amount of water up to 1 hour before the test (e.g., if you need to take your regular medication), but not more than 4 fl oz (100 mL).
- Do not smoke/use tobacco products (e.g. chewing tobacco, nicotine gum) before or during administration of GEBT.
- Do not undertake any vigorous activity within 8 hours prior to the test. During the test, limited walking is allowed, when necessary, e.g., use of restroom.
- The GEBT procedure should be performed in a comfortable environment. You should sit quietly, for the duration of the test. The whole test takes approximately 5 hours. You are allowed to read a book, watch TV, use a laptop/tablet.

Failure to follow all of these directions could result in inaccurate GEBT results!

Items/Information Required for Taking GEBT

- GEBT Kit (supplied by Cairn Diagnostics)
- Drinking Water
- Microwave
- Drinking Cup
- Plate
- Your Current Weight/Height
- 100% charged device (or plugged into power supply during the test) with internet access for telehealth administration, i.e. iPhone/Smartphone, Tablet/iPad, Laptop with audio/video capabilities
- A quiet place to sit for 5 hours
- Insurance Card and ID
- Glucometer (only if you are diabetic)

If you have any questions prior to taking your test, please refer to Cairn's website: www.cairndiagnostics.com.

You can also email or call (8am – 4pm Central Standard Time) our helpdesk:
[contact]
[contact] X 605

SPEC-CD-032, Patient Preparation Sheet (3 pages)

UNCONTROLLED COPY
Version May Not Be Current

CAIRN DIAGNOSTICS	DOC No. SPEC-CD-032.00
SPEC: Telehealth GEBT Patient Preparation Sheet	Page 1 of 2

Effective Date: NOV 05 2020

Material Title: Telehealth GEBT Patient Preparation Sheet	Material Code: L109
Material Description: GEBT information sheet for patients and physicians to review prior to enrolling a patient in the telehealth program.	
FDA approved Telehealth Patient Preparation Sheets are made up of the following:	

 1. Text that matches attached example. 2. Text printed in color. 3. Form printed on front of one sheet of 8 1/2" x 11", white paper (SPEC-QA-012, MatCode C010). 	
Supplier: Cairn Diagnostics	Supplier Material Code: L109
Expiration/Retest: N/A	Storage Conditions: Limited Access Storage
Sampling Plan:	

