4.0 STUDY GOALS AND OBJECTIVES

The purpose of this study is to establish the usability of a telehealth platform for the administration of GEBT. The objectives of this study are as follows:

- To demonstrate the safety of administering the ¹³C-Spirulina GEBT by telehealth by showing that there is no more than expected frequency of adverse events during administration of GEBT by a telehealth professional, than would be expected during administration of GEBT in a clinician's facility
- To demonstrate patient ability to prepare and administer the ¹³C-Spirulina GEBT, under the supervision of a telehealth professional, according to instructions
- To demonstrate patient ability to complete the GEBT test request form, under the supervision of a telehealth professional, according to instructions
- To demonstrate patient ability to collect GEBT breath samples under the supervision of a telehealth professional
- To demonstrate the ability to successfully ship kits/breath samples to/from home
- To demonstrate the ability of a telehealth platform to function correctly and be used correctly by virtually supervised patients

- **Note:** The steps and order of steps for tele-supervised GEBT administration is the same as that currently conducted in doctors' offices according to approved GEBT labeling.

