6.2 Administration of ¹³C-Spirulina GEBT

Administer the ¹³C-Spirulina GEBT to participants according to the instructions enclosed in the GEBT kit in the approved package insert and modified labeling under the supervision of a Cairn telehealth administrator as described in SOP-CD-028, Telehealth Administration Procedures (Exhibit E).

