7.0 RISK/SAFETY INFORMATION

7.1 Established Contraindications, Warnings and Precautions of GEBT

The following contraindications, warnings and precautions have been established for the ^{13}C -Spirulina GEBT in FDA-approved labeling:

- Individuals with known hypersensitivity to Spirulina, egg, milk or wheat allergens should avoid the GEBT
- Because the GEBT is an indirect multi-compartmental method of measuring gastric emptying, GEBT results may be inaccurate in individuals compromised with

significant small bowel, pancreatic, liver, and/or lung disease. Consequently, GEBT should not be administered to patients with pulmonary dysfunction (e.g. COPD) and/or small bowel malabsorption.

- Individuals with severe lactose intolerance may wish to avoid the GEBT, as the test meal contains a small amount of lactose, approximately 2.7 grams.
- The performance characteristics for individuals under the age of eighteen (18) years have not been established for this test.
- The performance characteristics for pregnant women have not been established for this test.
- False positive and false negative results can occur with this test.
- Follow the directions for collecting breath samples carefully. Errors in the timing and/or procedures for collecting breath samples may affect test results and necessitate retesting.
- The GEBT should not be performed in individuals who have taken medications known to influence the rate of gastric emptying (e.g. erythromycin, metoclopramide, opiates and anticholinergics) within three (3) days prior to testing. Individuals should stop such medications only after consulting with and obtaining approval from their attending physician or the physician ordering the test.
- Fasting serum glucose levels of diabetic subjects should be checked before administration of GEBT and the test should only be administered to subjects with a fasting serum glucose level of $<275\text{mg/dl}$.
- After 24 hours there is no residual $^{13}\text{CO}_2$ signal in the breath arising from the ^{13}C label contained in the GEBT meal; thus, the GEBT may be administered as frequently as every 24 hours.
- The GEBT should not be administered within 24 hours (or the relevant washout period) of other ^{13}C breath tests (e.g. the ^{13}C -Urea breath test for *H. pylori*).

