3.3 Initial Patient Contact – GEBT Scheduling

3.3.1 Once the Physician Order Form has been received and accepted, the CSM or CSR will call the patient to discuss scheduling the GEBT using the Welcome Call Script (Exhibit A).

3.3.2 The CSR/CSM will begin tracking patient contact using FORM-CD-036, Telehealth Patient Contact Form using information obtained during the call.

- Enter the patient name in the Patient Name field.
- Complete the GEBT ID once a kit has been selected for shipping.
- Enter the date of the Welcome Call.
- Enter the Client Services Representative Name (CSR) which is usually the person initially entering information in this form.
- Enter the Tele-administrator name.
- Complete the questions during the Welcome Call with the patient.
- Enter the appointment date and time for the scheduled GEBT.
- Enter the type of device that the patient proposes to use during the administration of the test.

3.3.3 Within one hour after the Welcome Call, the CSR/CSM completes the following activities:

3.3.3.1 Send an email using the Summary Email Template (Exhibit C) with the following information:

- A summary of the information discussed,
- Confirmation of the date and time for administration of the GEBT,
- Include the link to the information video and include the password "tummy." (<https://cairndiagnostics.com/healthcare-providers/telehealth-resources/> SPEC-CD-038, "GEBT Informational Video").

3.3.3.2 Send the patient the following text which includes the date and time for the administration of the GEBT and a link to the informational video.

NOTE: Change the underlined portion to the appropriate day, date, and time of the patient's test.

Text Message Template 1

Your GEBT is scheduled on (Tuesday, August 4, 2020 at 8 a.m. EST). Please watch the patient information video prior (link included below and, in your email) to the morning of your scheduled test. The password to view the video is "tummy." <https://cairndiagnostics.com/healthcare-providers/telehealth-resources/>

3.3.3.3 Enter appointment date and time on FORM-CD-036, Telehealth Patient Contact Form and initial and date when the confirmation text and email have been sent.

3.3.4 Schedule the "24-hour before the test" text reminder as seen below (change the underlined portion to the appropriate teleadministrator and the day, date, and time of the patient's test).

Text Message Template 2

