3.5 GEBT Administration – Initial Video Call

- 3.5.1 On the day of the GEBT, five (5) minutes before the scheduled administration, the Tele-Administrator (TA) sends the patient the following text and/or email (based on the patient's preference).

Text Message Template 5

"To begin your GEBT test, please select link in the next text."

- 3.5.2 Once this text has been sent, start the video call in TigerConnect (see SOP-CD-033 for starting the video session) and wait for the patient to join the session.
- 3.5.3 Follow the Telehealth Administration Call Script (Exhibit B) and complete the Telehealth Meal Administration Questionnaire & Checklist (FORM-CD-037).
 - 3.5.3.1 If any of the answers to the patient qualification questions are not satisfactory, then the test must be rescheduled.
 - 3.5.3.2 File the completed Telehealth Meal Administration Questionnaire & Checklist in the patient file once the test administration is completed.
- 3.5.4 After the patient completes the meal and records the times for post-meal breath samples, schedule text messages to be delivered five minutes before each scheduled

CAIRN DIAGNOSTICS	DOC No. SOP-CD-028.00
SOP: Telehealth Administration Procedures	Page 5 of 7

breath collection time. There will be six texts total, one each for the 45, 90, 120, 150, 180 and 240-minute time points.

Text Message Template 6 - 11

"GET READY: The (XX)-minute breath sample should be collected at (Scheduled time). Record the actual collection time on your test administration form."

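### The test-day script (SOP-CD-028 Exhibit B, step 7) does not stop a glucose reading of exactly 275 mg/dL, which the labeling restated in protocol section 7.1 would exclude

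*Protocol*

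**What the plan says.** **Labeling limit.** Protocol section 7.1 lists the precautions in the FDA-approved labeling. For diabetic subjects, fasting glucose is to be checked first, and "the test should only be administered to subjects with a fasting serum glucose level of" <275 mg/dL.

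**Test-day script.** SOP-CD-028 Exhibit B, step 7, asks whether the participant is diabetic and, if so, for that morning's glucose. The administrator's note is that if the "blood glucose level is >275 mg/dL, reschedule the test". SOP-CD-028 section 3.5.3.1 adds a general rule without a number: "If any of the answers to the patient qualification questions are not satisfactory, then the test must be rescheduled".

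**How the two are linked.** Protocol section 6.2 has the test given "according to the instructions enclosed in the GEBT kit in the approved package insert and modified labeling", supervised as SOP-CD-028 describes. Both sources therefore apply to the same test.

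**Companion questions.** Exhibit B, step 8, asks whether anyone is assisting that day: "If they are diabetic and this response is NO, reschedule the test". Question 4 of the welcome call (SOP-CD-028 Exhibit A) is narrower: "If you are an insulin dependent diabetic, will someone be able to accompany you, or check on you, during the test"? SOP-CD-028 section 3.3.1 gives the trigger for that call: "Once the Physician Order Form has been received and accepted, the CSM or CSR will call the patient to discuss scheduling the GEBT".

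**The concern.** The glucose limit is a labeled precaution, and step 7 is where it is put into practice: the administrator hears the reading and decides whether to go on. A script with a looser bound than the labeling can let through a participant whom the labeling would turn away. Section 14.0 of the protocol says the data will be used to confirm that telehealth carries no more risk than administration under the approved labeling. The script should therefore not be more permissive than that labeling, even at one value.

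The companion questions raise a smaller matter. Two screens for the same need use different populations and different wording, so a participant could clear the scheduling screen and be turned away on the day.

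**Working it through.** No sample-size, power or error-rate calculation is involved. The check compares the rules value by value.

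**1. Glucose.** Write g for the reading in mg/dL, and treat the labeling's fasting serum value and the script's reading that morning (taken after step 6 has confirmed the fast) as the same quantity.

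- Section 7.1 permits the test when g < 275. Its complement, the set to be turned away, is g ≥ 275.
- Step 7 reschedules when g > 275. The set it does not stop is g ≤ 275.
- The rules differ where g ≤ 275 and g ≥ 275 both hold, that is, at g = 275 only.

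| Reading (mg/dL) | Section 7.1 | Step 7 | Agree? |
|---|---|---|---|
| 274 | permitted | not stopped | yes |
| 275 | not permitted | not stopped | no |
| 276 | not permitted | rescheduled | yes |

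With step 7 changed to g ≥ 275, the set not stopped becomes g < 275, which is the labeling's permitted set exactly.

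**2. Does another rule in the SOP close the gap?** Section 3.5.3.1 requires rescheduling on an unsatisfactory answer but does not say which glucose value is unsatisfactory. Step 7 is the only glucose cut-off the SOP shows. FORM-CD-037, which the administrator completes alongside the script, is not in the copy reviewed, so its cut-off cannot be checked.

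**3. Companion, where the welcome call is used.**

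| Participant | Question 4 | Step 8 | Same outcome? |
|---|---|---|---|
| Insulin-dependent, someone assisting | pass | pass | yes |
| Insulin-dependent, nobody | stop | reschedule | yes |
| Diabetic not on insulin, someone assisting | not applicable | pass | yes |
| Diabetic not on insulin, nobody | not applicable | reschedule | no |

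A fifth case is an insulin-dependent participant with someone who will only check in. That participant passes question 4, but the result at step 8 depends on what assisting means, which the script does not define. Read literally, it is a second difference.

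In the fourth row the later screen is the stricter one. Steps 7 and 8 both come before the kit seal is broken at step 16, so the kit is not used up. A new date must fall within two weeks of Visit 1 (section 6.1) as well as within two weeks of kit receipt (section 10.0). Only enrolled participants receive kits, so the Visit 1 limit would ordinarily expire first.

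**The case against.** The strongest reply is that step 7 is silent at 275 and does not tell the administrator to test. The package insert still applies through section 6.2, and section 3.5.3.1 allows rescheduling on an unsatisfactory answer, so someone following all three sources can reschedule at 275 without breaching the script. This stands as mitigation. A reader might infer that the script orders a test the labeling forbids, and the documents do not support that. The gap remains because the only number in the SOP is the looser one.

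A reader might also take the note in section 4.0 as proof that the looser cut-off was unintended: "The steps and order of steps for tele-supervised GEBT administration is the same as that currently conducted in" doctors' offices. The note speaks to steps and their order, not to numerical limits, so it does not settle intent.

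On the companion questions, a reader might infer a contradiction or a safety gap. Neither is supported. Question 4 does not tell other diabetics that they may test alone, and a stricter final screen is a legitimate design. Any diabetic who answers no at step 8 is rescheduled. It is also not shown that study participants receive the welcome call: it follows a physician order, whereas participants enter through Visit 1. If they do not receive it, there is no second question to conflict with step 8. The preparation sheet, brochure and warnings sheet are not readable in the copy reviewed and may already give notice of the requirement.

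**Conclusion.** The glucose point holds, at minor severity. Step 7 fails to stop one boundary value, 275 mg/dL, that the labeling restated in section 7.1 excludes. If readings are reported in whole mg/dL, that is a single possible reading. The number of participants affected cannot be computed, because the documents give neither the share of participants who will be diabetic nor the distribution of their glucose values. No endpoint, acceptance criterion or analysis depends on the cut-off.

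This rests on the strict inequality in section 7.1 being the labeling's actual wording, and on no unseen form already carrying the right bound. If FORM-CD-037 does carry ≥275, step 7 still needs correcting to match it.

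The companion difference is secondary and conditional on participants receiving the welcome call. At worst it causes an avoidable reschedule on the test day for a participant who has already fasted.

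**What to change.** In SOP-CD-028 Exhibit B, step 7, replace the bound so that the test is rescheduled at a blood glucose of ≥275 mg/dL. Check FORM-CD-037 Section 1 Question 6 and make the same change there if it uses the same cut-off. The cost is a wording revision to the script and possibly one form, with no change to design, sample size or analysis.

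Optional tidying: if participants do receive the welcome call, use one diabetic population and one description of the companion in both Exhibit A question 4 and Exhibit B step 8. Any diabetic is the natural default, unless the sponsor's clinicians narrow both. If the unseen patient materials do not already state the requirement, tell diabetic participants at Visit 1 or at scheduling.
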